6.2.1. Exposure Adjusted incidence rates (EAIR)

Exposure-adjusted incidence rates (EAIRs) of treatment-emergent adverse events (TEAEs) will be presented by treatment group, MedDRA System Organ Class (SOC), and preferred term, as well as by treatment group and MedDRA preferred term. For each treatment group, the EAIR of a specific treatment-emergent event is defined as the number of subjects experiencing the event at least once, divided by the total exposure-adjusted follow-up time in person-years. EAIRs will be presented as incidence rates per person-years of follow-up.

For subjects who experience the event, the exposure-adjusted follow-up time will be calculated from the first exposure (to PTC857 or Placebo) until the first occurrence of the event. For subjects who do not experience the event (censored), the follow-up time will be calculated from the first dose until their last safety follow-up date while on Part A. This could either be the date of completion of Part A safety follow-up, the date of death if the subject died before experiencing the event, or the date of last on-treatment follow-up if the subject was lost to follow-up.

Missing or partial AE onset dates will be imputed using the imputation rules described in Section 12 (Appendix 2).

6.2.2. Adverse Events Indicative of ALS Disease Progression

TEAEs that are indicative of ALS disease progression will be tabulated by treatment arm. The following list of MedDRA preferred terms will be used to define TEAEs that are indicative of disease progression.

Acute respiratory failure	Increased bronchial secretion	Salivary hypersecretion
Affect lability	Increased upper airway secretion	Suicidal ideation
Amyotrophic lateral sclerosis	Muscle spasms	Upper respiratory tract infection
Asthenia	Muscle spasticity	Urge incontinence
Balance disorder	Muscular weakness	Urinary retention
Cardio-respiratory arrest	Musculoskeletal stiffness	Urinary tract infection in males
Death	Myalgia	Urinary tract inflammation in males
Dysgraphia	Neurogenic bladder	Viral upper respiratory tract infection
Dysphagia	Oral candidiasis	Vocal cord paralysis
Dyspnoea	Oral fungal infection	Weight decreased
• Fall	Respiratory failure	
Fatigue	Respiratory tract congestion	
Hypotonia	Respiratory tract infection	
Hypoxia	Respiratory tract infection viral	

6.2.3. Disproportionate rate of Disease Progression by Treatment Received

To evaluate whether treatment with PTC857 may accelerate ALS disease progression, an analysis of participants with a disproportionate rate of disease progression by treatment assignment will be performed to further inform benefit-risk assessment. For this analysis the number and percent of subjects with declines in ALSFRS-R that are greater than or equal to 18 points at the 24-week visit will be tabulated by treatment arm.

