^a The Baseline Visit will be defined as Day 1 of the study. Baseline Visit procedures may be performed within the 3 days before the day that study drug is first administered. The day in which the first dose of study drug is administered will be Day 1. For subjects taking part in the PK Sub-Study, the PK laboratory tests must be completed on the same day as the first dose of study drug.

^b Day 169 will be considered the End of Treatment Visit only for those who choose not to enter the LTE Period (Part B).

^c Follow-up Visit on Day 197 only for subjects who choose not to enter the LTE Period (Part B).

^d For subjects who terminate early from the study and consent to continued follow-up, the investigator should attempt to gain vital status on the participant and conduct the ALSFRS-R assessment approximately every 28 days for the remaining duration of the study, in accordance with local requirements/regulations.

- e The Day 29 Visit will be conducted in-person for subjects participating in the PK Sub-Study only.
- f For the telephone call/in-home visits, where applicable, the ALSFRS-R, C-SSRS, adverse events, and prior/concomitant medications assessments will be conducted via a telephone call. Vital signs assessments and samples for clinical laboratory tests will be collected via a home health nurse during applicable inhome visits at the subject's home during these visits. Subjects may go to the site for an in-person visit at the discretion of the PI. Visits indicated as in-person only may be conducted remotely (ie, in-home) following discussion between the site and the medical monitor. In-person visits that are conducted remotely must include the following assessments, at minimum (if such assessments are typically included during the visit): serum/urine pregnancy test (females only), vital signs, clinical laboratory tests, ALSFRS-R, C-SSRS, adverse events, prior/concomitant medications, sparse PK blood sampling, laboratory biomarkers, and ALSAQ-40.
- ⁹ The ICF for Part B should be provided to the subject at the Day 85 visit to allow the subject adequate time to consider transitioning into Part B.
- ^h The ICF for Part B should be signed by the subject at the Day 169 visit if they choose to enroll into Part B.

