1.5. Sample Size

For the primary efficacy endpoint, the combined assessment of ALSFRS-R and survival after 24 weeks of treatment, 307 subjects in the ITT1 Analysis Set (205 in the PTC857 group and 102 in the placebo group, based on a 2:1 randomization ratio) will provide approximately 85% power to detect a treatment difference of 2 points with a standard deviation of 5.3, based on a 2-sided 0.05 level Joint Rank Test, and assuming 24-week survival rates of 96.5% and 95% in the PTC857 and placebo groups, respectively. These assumptions took into consideration data from 2 clinical

studies in ALS which reached statistical significance for their primary endpoints that reported overall death rates of 0% and 5% (Edaravone (MCl-186) ALS 19 Study Writing Group 2017 and Paganoni, 2020) A standard deviation of 5.3 points for the ALSFRS-R score at Week 24, among treated subjects was reported for the edaravone study (Edaravone (MCl-186) ALS 19 Study Writing Group 2017).

Assuming approximately 10% of randomized subjects will not meet the ITT1 Analysis Set definition, then approximately 340 subjects will be randomized to ensure that 307 subjects are randomized into the ITT1 Analysis Set. Given that the primary analysis incorporates deaths as a combined endpoint, and a fully imputed analysis dataset is utilized in the analysis, additional enrollment and randomization to make up for discontinued subjects is not planned. This document clarifies a typographical error in the study protocol that incorrectly indicated a treatment difference of 2.5 points instead of 2 points, is of interest.

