3. GENERAL CONSIDERATIONS

3.1. General Considerations

Continuous data will be summarized using number of observations (n), arithmetic mean (mean), standard deviation (SD), median, minimum value (min) and maximum value (max) by treatment group. Additionally, for biomarker data, the summaries will include geometric means and standard deviations, as appropriate. Categorical variables will be summarized using the frequency count (n) and percentage (%) by treatment group. An overall/total group (i.e., sum of all treatment groups) will generally be presented additionally for summaries of disposition, demography, and baseline characteristics.

For all percentage calculations, the denominator will be the number of subjects in the analysis set for the treatment group, unless otherwise stated.

Only data from protocol scheduled visits will be included in the summary tables. Data from unscheduled visits will not be included in the summary tables but will be included in the by-subject listings. Descriptive summaries by visit and treatment will be provided for all the primary and secondary efficacy endpoints.

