4.9. Visit Windows for The Early Termination Visit and Unscheduled Visits

If a subject completely withdraws from the study prematurely, and unless consent is withdrawn, all efforts are made to collect efficacy and safety data and to complete the Early Termination Visit (ET).

Follow-up efficacy data collected at the early termination visit will be incorporated into the study visit schedule using the visit windows, defined in Table 1 and Table 2. Similarly, follow-up efficacy data collected during unscheduled visits or make-up visits will also use the same visit windows. If a follow-up visit (ET) or unscheduled visit falls in the same visit window as a scheduled visit, then the scheduled visit data will be used. If an unscheduled visit and ET visit fall within the same window, then the visit closest to the target day will be used.

Table 1: Visit Windows for Early Termination and Unscheduled Visits

	ALSFRS-R		
Visit	Lower Bound	Target Day	Upper Bound
Day 29	15	29	42
Day 57	43	57	70
Day 85	71	85	98
Day 113	99	113	126
Day 141	127	141	154
Day 169	155	169	182

Table 2: Visit Windows for Early Termination and Unscheduled Visits

	SVC, ALSAQ-40, Norris Scale, and plasma NfL		
Visit	Lower Bound	Target Day	Upper Bound
Day 85	64	85	106
Day 169	148	169	190

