6. SAFETY ANALYSES

All analyses described in this section will be performed on the Safety Analysis set and will be presented by treatment group (actual treatment received PTC857 vs Placebo). The results will be descriptive in nature. There will be no statistical comparisons between the treatment groups for safety data, unless otherwise specified within the relevant section. All data will be summarized and listed.

Safety assessments will include adverse events, laboratory assessments, vital signs, 12-Lead electrocardiogram, physical examination, and Columbia-Suicide Severity Rating Scale (C-SSRS).

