- Confidence intervals are displayed within round brackets and separated by a comma. The lower limit is presented first, and the upper limit is presented second. The confidence interval is placed either beside or below the corresponding estimate. The estimate and the confidence limits are presented using the same degree of precision.

- P-values will be output in the format: '0.xxx', where xxx is the value rounded to 3 decimal places. Every p-value less than 0.001 will be presented as <0.001. If the p-value is returned as >0.999, then present as >0.999.
- Percentage values will be printed to one decimal place. Unless otherwise noted, for all percentages, the number of subjects in the analysis population for the treatment group who have an observation will be the denominator. Percentages after zero counts will not be displayed and percentages equating to 100% will be presented as 100%, without decimal places.
- Tabular display of data for medical history, prior/concomitant medications, and all tabular displays of adverse event data will be presented by the body system, treatment class, or SOC with the highest occurrence in the active treatment group in decreasing order, assuming all terms are coded. Within the body system, drug class and SOC, medical history (by preferred term), drugs (Medication class), and adverse events (by preferred term) will be displayed in decreasing order. If incidence for more than 1 term is identical, they will then be sorted alphabetically.
- Missing descriptive statistics or p-values which cannot be estimated will be reported
 as '-' Missing values for numeric and character variables are displayed as blanks in
 data listings.
- The percentage of subjects will normally be calculated as a proportion of the number of subjects assessed in the relevant treatment group (or overall) for the analysis population presented. However, careful consideration is required in many instances due to the complicated nature of selecting the denominator, usually the appropriate number of subjects exposed. Details will be described in footnotes or programming notes, as necessary.
- If no relevant data are available at all for a display, then present "No data to Report".

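### The SAP 6.2.3 table on accelerated progression cannot count a death before Week 24, or an 18-point loss followed by exit without a Week 24 score, as an event

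*SAP*

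**What the plan says.** All section numbers refer to the Part A SAP unless the protocol is named.

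- **Purpose and event.** Section 6.2.3 opens with "To evaluate whether treatment with PTC857 may accelerate ALS disease progression". It then tabulates "the number and percent of subjects with declines in ALSFRS-R that are greater than or equal to 18 points at the 24-week visit" by treatment arm. It gives no rule for deaths, for a missing Week 24 score, or for an 18-point loss seen earlier.
- **Population.** Section 6 states: "All analyses described in this section will be performed on the Safety Analysis set".
- **Denominator.** Two general rules conflict. Section 3.1 says: "For all percentage calculations, the denominator will be the number of subjects in the analysis set for the treatment group, unless otherwise stated". Section 9 says that, unless otherwise noted, "the number of subjects in the analysis population for the treatment group who have an observation will be the denominator". Section 6.2.3 does not choose between them.
- **Early termination scores.** Under Section 4.9, "Follow-up efficacy data collected at the early termination visit will be incorporated into the study visit schedule using the visit windows". The Day 169 window for ALSFRS-R is Day 155 to 182, and the rule is written for efficacy data.
- **Follow-up of leavers.** For early terminators who consent, protocol Table 1 (Section 3.2, footnote d) asks the investigator to seek vital status and "conduct the ALSFRS-R assessment approximately every 28 days for the remaining duration of the study".
- **Imputation.** Sections 4.7 and 5.5.1.2 specify multiple imputation for the CAFS and ALSFRS-R efficacy analyses. It is not extended to 6.2.3.

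**The concern.** If a drug speeds up ALS, some of the subjects it harms most will die or become too ill to continue before Week 24. A table that needs a Week 24 score loses those subjects because of the very outcome it is meant to detect. Someone who has lost 18 points by Day 85 and then dies is the clearest possible case of rapid progression, and cannot appear in the numerator.

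The SAP handles this better elsewhere. CAFS ranks every death below every survivor (3.2.14). Laboratory shift tables use the worst on-treatment value (6.3), and the overall C-SSRS assessment takes the worst finding in the period (6.7). The acceleration table alone relies on a single late visit with no rule for death. What is at stake is a benefit-risk table that could look balanced while deaths are not.

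**Working it through.** The documents give no expected rate, sample size or power for this table, so there is no planned figure to reproduce.

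**Step 1: where an early death or exit goes.** Under Section 3.1 the subject stays in the denominator as a non-event. Under Section 9 the subject leaves both numerator and denominator. Under neither is the subject an event. An early termination score before Day 155 does not map to Week 24.

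**Step 2: expected deaths.** Section 1.5 plans "assuming 24-week survival rates of 96.5% and 95% in the PTC857" and placebo groups respectively, for ITT1. Section 1.1 gives about 340 randomized 2:1, so about 227 and 113.

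- ITT1: 205 × 0.035 = 7.2 active; 102 × 0.05 = 5.1 placebo; total 12.3.
- All 340, applying the ITT1 rates to everyone: 226.7 × 0.035 = 7.9 active; 113.3 × 0.05 = 5.7 placebo; total 13.6.

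**Step 3: expected counted events.** I take the Week 24 decline among survivors as normal with SD 5.3 (the value in Section 1.5) and a cut at 17.5, because scores are whole numbers. The documents give no mean decline, so I assume placebo means of 4 to 10 points, with either no drug effect or a 2-point benefit. P = 1 − Φ((17.5 − mean)/5.3), applied to 218.7 active and 107.7 placebo survivors. Uncounted share = 13.6 / (13.6 + counted events).

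| Assumed placebo mean decline | Counted, no effect | Uncounted share | Counted, 2-point benefit | Uncounted share |
|---|---|---|---|---|
| 4 | 1.8 | 88% | 1.0 | 93% |
| 6 | 4.9 | 74% | 2.8 | 83% |
| 8 | 11.9 | 53% | 7.2 | 65% |
| 10 | 25.6 | 35% | 16.4 | 45% |

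**Step 4: sensitivity to fast screeners.** About 340 − 307 = 33 Safety Set subjects fall outside ITT1, mainly because they lost more than 4 points in screening. If their mean 24-week loss is assumed to be 10 to 15 points (SD 5.3, 96% survival), they add 33 × 0.96 × 0.0785 = 2.5 to 33 × 0.96 × 0.3186 = 10.1 counted events. With the others at 10 points, the fast group at 15 and no drug effect, counted events are 294.7 × 0.0785 + 10.1 = 33.2 and deaths are 12.3 + 1.3 = 13.6. The share is then 13.6/46.8 = 29%.

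**Step 5: what the table would show.** This assumes 227 and 113 subjects, 3% fast decline among those assessed (rounded to whole subjects), and no missing data other than deaths.

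| Deaths, active vs placebo | Section 3.1 denominator | Section 9 denominator | Deaths also counted as events |
|---|---|---|---|
| 16 vs 6 | 6/227 = 2.6% vs 3/113 = 2.7% | 6/211 = 2.8% vs 3/107 = 2.8% | 22/227 = 9.7% vs 9/113 = 8.0% |
| 23 vs 6 | 6/227 = 2.6% vs 3/113 = 2.7% | 6/204 = 2.9% vs 3/107 = 2.8% | 29/227 = 12.8% vs 9/113 = 8.0% |

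The table as written stays flat while deaths on active nearly triple from the planned 8 to 23.

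**The case against.** The defence has real substance on four points.

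1. **These subjects are not necessarily classed as slow progressors.** A reader might infer that they are. That holds only under the Section 3.1 denominator; under Section 9 they are left out altogether.
2. **Leaving early does not by itself remove a subject.** A reader might infer that all leavers are lost. Subjects who stop drug are to stay in the study (protocol 3.7, 4.6 and 6.4), consenting early terminators are to be assessed about every 28 days, and an early termination score from Day 155 to 182 may map to Week 24. The firm gap is deaths, plus leavers with no late score.
3. **The whole safety conclusion is not biased.** A reader might infer that too. Deaths are shown by arm in the survival analysis (5.7), in the fatal adverse event table (6.2) and among the progression-type events (6.2.2), and CAFS incorporates them. Excess deaths on PTC857 would be visible there. Section 6.2.3 is supplementary and descriptive.
4. **No single uncounted share can be quoted.** The result depends on a mean decline the documents do not give. One of the two planning studies reported no deaths, and with none nothing would be missed through death. Not every death reflects rapid progression.

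All four limit the claim without removing it. Section 6.2.2 mixes death with terms such as fatigue and myalgia, and the survival analysis carries no functional loss. No planned output counts subjects who died or lost 18 points, or picks out an 18-point loss before an early exit. It is also fair to say that an any-visit rule still misses a leaver who was on that pace but had not yet lost 18 points.

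**Conclusion.** The point holds for this one table. As written, Section 6.2.3 cannot register a death before Week 24, or an 18-point loss followed by exit without a Week 24 score, and its denominator is unresolved. The table can therefore be biased toward no harm on the question it was added to answer.

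About 14 of 340 subjects would die uncounted at the planned rates, assuming the ITT1 survival figures apply to the whole Safety Set. Their share of all who died or lost 18 points or more is roughly 35% to 93% for assumed mean declines of 10 down to 4 points with SD 5.3, and lower (29% in one case shown) if fast screeners go on declining faster. The direction is secure; the share rests on assumption. It is worth correcting because the table is meant to inform benefit-risk and the change is cheap.

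**What to change.** Keep the current Week 24 row. Add a row counting any subject who, by Week 24, has died or has had an ALSFRS-R loss of 18 points or more at any Part A visit, including early termination and post-withdrawal follow-up. Use all Safety Set subjects as its denominator, and state which denominator governs the existing row. Show the two components (death; loss of 18 or more) separately, and give the number without a Week 24 score in each arm.

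The cost is a sentence or two in the SAP and a few table lines. No new data are needed, since ALSFRS-R is scheduled at Days 29, 57, 85, 113, 141 and 169 and at early termination. Because Section 3.1 keeps unscheduled data out of summary tables, the text should say that off-schedule scores count here. The drawback is that all-cause deaths unrelated to progression enter the combined row; the component rows make that visible.

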6.3. Laboratory Values

All clinical laboratory analyses will be performed by the central laboratory. The clinical laboratory assessment of hematology, clinical chemistry, and urinalysis will be obtained at scheduled visits. The following parameters are collected during the double-blind period at the specified visits as per protocol:

Parameter(s)	Scheduled Visit(s)
Hematology: Hemoglobin, Hematocrit, RBC count,	Screening, Day 1, Day 29, Day 57, Day
Reticulocytes, Platelet count, WBC count, Neutrophils,	85, Day 169, Day 197, ET
Eosinophils, Monocytes, Basophils, Lymphocytes, Mean	
corpuscular volume	
Clinical Chemistry: Urea, Creatinine, Fasting glucose,	Screening, Day 1, Day 29, Day 57, Day
Sodium, Potassium, ALT, AST, GGT, Bilirubin (total,	85, Day 169, Day 197ET
direct/indirect), Alkaline phosphatase, Albumin,	
Lipid Profiles: Cholesterol (total), LDL, HDL, Triglycerides,	Screening, Day 1, Day 14, Day 29, Day
LDH	57, Day 85, Day 169, Day 183, Day 197,
	and ET
Urinalysis: Urobilinogen, Nitrite, pH, Glucose, Total	Screening, Day 1, Day 85, Day 169, and
protein, Erythrocytes, Leukocytes, Ketones, Microscopy,	ET
Specific gravity, Bilirubin	
Coagulation: PT [sec], PT [INR], aPTT	Screening, Day 1, Day 29, Day 57, Day
	85, Day 169, Day 197, and ET
Pregnancy Test: β-HCG, FSH	Screening, Day 1, Day 29, Day 57, Day
	85, Day113, Day141, Day 169, Day 197,
	and ET
Note: Follow-up Visit on Day 197 is only for subjects who choose not to en	ter the LTE Period (Part B).

Separate summary tables and listings will be produced for each of the separate groups above (e.g., separate table for hematology and clinical chemistry etc.); however, urinalysis, and serum and urine pregnancy tests will be listed only. The International System of units (SI units) will be used for all summary and data listing displays unless otherwise indicated.

Laboratory data will be summarized descriptively by visit for each laboratory parameter by treatment group and overall. Both observed results and changes from baseline will be summarized for continuous variables. Laboratory values will be categorized as clinical grade (low/normal/high) according to normal ranges. Shifts from baseline to the last on-treatment grade and the worst on-treatment grade will be presented. For these shift summaries, for the last on-treatment summary only scheduled visits will be taken; for the worst on-treatment summaries unscheduled assessments will be included in the assessment of worst. Both worst low and worst high will be summarized.

Laboratory values that are below the limit of quantification will be imputed as the lower-limit of quantification, similarly, values above the limit of quantification will be imputed as the upper-limit of quantification for the summary statistics. But for listings, the values will be presented as recorded.

By-subject listings of all the laboratory parameters will be presented that clearly indicate out of normal range values and possible abnormal values for the safety analysis set.

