|---|--------------------|---------|-----------------------|--------|----------------------|--------------------|------------|--------------------|--------------------|----------------------------------|----------------------------|----------------------|
| | | | | (24 W) | | | | | | | | |
| Study Day | Screening | Day -28 | Day 1 | Day 14 | Day 29 | Day 57 | Day 85 | Day 113 | Day 141 | Day 169 | Day 197 | |
| | (-56 Days) (±5) | (±3) | (- 3) ª | (±3) | (±3) | (±3) | (±3) | (±3) | (±3) | (±3) | (±3) | |
| | | | Baseline ^a | | | | | | | End of Treatment ^b | Follow- Up ^c | ET₫ |
| Telephone call/in-home or in-person visit ^f | IP | PC | IP | PC/IH | PC/IH ^{e,f} | PC/IH ^f | IP | PC/IH ^f | PC/IH ^f | IP | PC | IP |
| COVID-19 PCR | Х | | | | | | | | | | | |
| Informed consent | Х | | | | | | Xg | | | Xh | | |
| Inclusion/exclusion criteria | Х | | | | | | | | | | | |
| Re-evaluation eligibility | | | Х | | | | | | | | | |
| Randomization | | | Х | | | | | | | | | |
| Height | Х | | | | | | | | | | | |
| Weight and BMI | Х | | Х | | | | Х | | | Х | | Х |
| Demographics | Х | | | | | | | | | | | |
| Medical history | Х | | | | | | | | | | | |
| Serum/urine pregnancy test (females only) ⁱ | Х | | Х | | Х | Х | Х | Х | Х | Х | Х | Х |
| FSH measurement ^j | Х | | | | | | | | | | | |
| 12-Lead ECG ^k | Х | | Х | | | | Х | | | Х | | Х |
| Vital signs | X | | Х | | Х | Х | Х | Х | Х | Х | | Х |
| Physical exam ^m | X | | Х | | | | Х | | | Х | | Х |
| Sparse PK blood sampling ⁿ | | | X | | | | Х | | | X | | X |

| | | | Treatment Period (24 W) | | | | | | | EOS/ FU | Early Termination | |
|--|--------------------|---------|-------------------------|--------|--------|--------|--------|---------|---------|----------------------------------|----------------------|-----|
| Study Day | Screening | Day -28 | Day 1 | Day 14 | Day 29 | Day 57 | Day 85 | Day 113 | Day 141 | Day 169 | Day 197 | |
| | (-56 Days) (±5) | (±3) | (-3)ª | (±3) | (±3) | (±3) | (±3) | (±3) | (±3) | (±3) | (±3) | |
| | | | Baseline ^a | | | | | | | End of Treatment ^b | Follow- Up° | ET₫ |
| Clinical laboratory tests ^o | Х | | Х | Xp | Х | Х | Х | | | Х | | Х |
| CSF for biomarkers ^{q,r} | | | Х | | | | | | | Х | | Х |
| Laboratory biomarkers (blood and urine)s | | | Х | | | | Х | | | Х | | Х |
| ALSFRS-R ^t | Х | Х | Х | | Х | Х | Х | Х | Х | Х | Х | Х |
| PFTs ^u | Х | | Х | | | | Х | | | Х | | Х |
| ALS CBS | Х | | Х | | | | Х | | | Х | | Х |

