e Subjects who decide to enter the LTE Period should sign the consent form before the start of the LTE Period.

- The ICF for Part C should be provided to the subject at the Day 253 visit to allow the subject adequate time to consider transitioning into Part C.
- ⁹ The ICF for Part C should be signed by the subject at the Day 365 visit if they choose to enroll into Part C.
- h Women of childbearing potential will undergo monthly urine pregnancy testing on Days 197, 225, 253, 281, 309, 337, and 365, and at the Follow-up Visit. If a urine pregnancy test is positive, a serum pregnancy test will be conducted for confirmation and dosing should be immediately suspended and evaluated for continued study participation based upon the result of the serum pregnancy test and in discussion with the medical monitor. For months where an on-site visit is not scheduled, subjects will complete a urine pregnancy test at home, if local requirements allow, to be reported to the investigator and documented in the eCRF. Single 12-lead ECG measurements will always be performed prior to the dose of medication administered at the clinic. Subjects should be resting for at least 5 minutes in supine position prior to 12-lead ECG procedures.
- J Vital signs will consist of measurements of supine blood pressure, heart rate, body temperature, and respiratory rate. Vital sign measurements will be collected after the subject has been resting for 5 minutes. Blood pressure and heart rate measurements will be performed with subjects in a supine position, except when they semi reclined because of study procedures and/or AEs (eg, nausea, dizziness) or if deemed necessary by the PI or designee.
- ^k A targeted physical examination, including neurological examination, will be completed at all timepoints.
- Blood samples for PK evaluation will be collected from all subjects at predose only.
- ^m Clinical laboratory tests will consist of fasting lipid profile, hematology, coagulation, blood chemistry, and urinalysis. Urinalysis will only be performed at in-person clinic visits (ie, Day 253 and Day 365).
- ⁿ Clinical laboratory tests on Day 183 will consist only of a fasting lipid profile. Hematology and blood chemistry will not be evaluated during this visit.
- ^o Laboratory (blood and urine) biomarkers (aligned with the timing for the clinical laboratory tests) as per Section 7.1.7. Urine creatinine should be tested when urine p75NTR is sampled.

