3.2.5. Treatment Periods

Period	Definition	
Pre-treatment	Date of Screening through one day prior Date of first dose	
Double-blind	Date of first dose through to Date of last dose during Part A	
Treatment Period	or	
	Date of first dose through to one day prior first dose during open-label treatment	
	period	

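### Part A SAP 6.3 lists Day 183 lipids and Day 197 blood tests as double-blind laboratory visits, but the protocol schedules them only in open-label Part B

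*SAP*

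**What the plan says.** Section 6.3 of the Part A SAP introduces its laboratory visit table with this statement: "The following parameters are collected during the double-blind period at the specified visits as per protocol". The lipid row of that table contains "Day 85, Day 169, Day 183, Day 197". The hematology, chemistry and coagulation rows also carry Day 197. A note under the table reads, in part, "Follow-up Visit on Day 197 is only for subjects who choose not to" enter Part B. There is no note on Day 183.

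The same section then sets the summary rule: "Laboratory data will be summarized descriptively by visit for each laboratory parameter by treatment group and overall". It adds shift tables from baseline to the last and the worst on-treatment grade. The last-grade shift uses scheduled visits only; the worst-grade shift also takes unscheduled results.

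Section 3.2.5 of the same SAP gives, as one form of the double-blind period, "Date of first dose through to one day prior first dose during open-label treatment" begins. In protocol section 3.2, a footnote to Table 2 (Part B) says: "Clinical laboratory tests on Day 183 will consist only of a fasting lipid profile".

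**The concern.** The list claims to follow the protocol's double-blind schedule and does not. Day 183 cannot hold a scheduled Part A value, because no subject has a scheduled test on that day without having moved to open-label PTC857.

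Lipids are the parameter for which this matters most. Protocol section 1.5.3 names lipoprotein changes as the one potential risk recognised so far, and section 1.5.1 reports reversible lipid changes after short exposure in healthy volunteers. The protocol's amendment history (Version 2.0) says the Day 14 and Day 183 visits were added so that lipids could be assessed 14 days after PTC857 is started. For a subject randomised to placebo, the Day 183 sample therefore measures an early drug effect. Shown under Placebo, it would blur the controlled comparison it was meant to inform.

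**Working it through.** The SAP states no figure to reproduce. The check sets the schedules side by side.

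**Step 1. Blood-test visits after Day 141**

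| Source | Day 169 | Day 183 | Day 197 |
|---|---|---|---|
| Part A SAP 6.3, lipids | yes | yes | yes |
| Part A SAP 6.3, hematology, chemistry, coagulation | yes | no | yes |
| Protocol Table 1 (Part A), laboratory row | yes | no such visit | none; telephone contact |
| Part A SAP Appendix 1, laboratory row | yes | no such visit | none; telephone contact |
| Protocol Table 2 (Part B), laboratory row | none | lipids only | yes |

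The visits in SAP 6.3 that are missing from Table 1 are Day 183 for lipids, and Day 197 for lipids, hematology, chemistry and coagulation. All of them are Part B laboratory visits. Day 197 in the pregnancy-test row is not a mismatch, because Table 1 schedules that test.

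**Step 2. Treatment at those visits**

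Protocol section 3.2 puts every Part B subject on open-label PTC857, and Table 2 dispenses study drug at Day 169. Taking Day 169 as the start:

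- Day 183 − Day 169 = 14 days on PTC857
- Day 197 − Day 169 = 28 days on PTC857

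The Parts B/C SAP (section 3.2.2) agrees: for subjects starting PTC857 in Part B, it maps Day 183 to week 2 and Day 197 to week 4 since first exposure.

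**Step 3. What the SAP's own rules do with each visit**

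- *Day 197.* The table note limits this visit to subjects who do not enter Part B. Table 1 draws no blood from them that day, so the four blood-test cells would be essentially empty.
- *Day 183.* No note applies. Section 3.2.5 would exclude these values, but section 6.3 neither cites it nor defines on-treatment. Because the shift to last grade takes scheduled visits, and Day 183 is listed as one, a program built from the list alone could use it.

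**Step 4. Comparison with the other safety sections**

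The adverse event section (6.2) stops explicitly before the LTE starts. The vital signs list (6.4) ends at Day 169 or early termination, although Table 2 also schedules vital signs at Day 197. The laboratory list is the exception.

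**Step 5. Upper bound on subjects involved**

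With 2:1 randomisation, 340/3 ≈ 113 subjects are on placebo. Only those who enter Part B have Day 183 lipids scheduled, and the documents do not give that number.

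**The case against.** A reader might infer that former placebo subjects taking PTC857 will be reported as placebo at both visits and in all four blood panels, and that their last on-treatment grade will move from Day 169 to Day 197. The documents do not support this:

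- The note under the table keeps Part B subjects out of the Day 197 visit. That leaves the cells empty rather than contaminated, and it disposes of the claim for hematology, chemistry and coagulation, whose only extra visit is Day 197.
- Section 3.2.5 closes the double-blind period before the first open-label dose. Section 1 of the SAP sends Parts B and C to a separate plan, and protocol section 8.4 limits the Part A analysis to data up to the Week 24 visit.
- Section 6 presents safety by actual treatment received, so an on-drug value labelled Placebo would contradict the stated principle.
- The Parts B/C SAP already lists both visits and reports these subjects in a separate Placebo/Utreloxastat column.

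The revision history says Version 2.0 narrowed the SAP from all parts to Part A. Leftover visit labels are a plausible explanation, though that is inference.

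Most of this stands, and it reduces the consequence from a planned misreporting to a programming risk. It does not rescue the list: if section 3.2.5 governs, Day 183 should not be there. The risk is also practical. Section 3.3 of the Parts B/C SAP summarises all available extension safety data at the Part A lock, so the open-label values will be at hand when the Part A tables are run.

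**Conclusion.** The contradiction is certain: SAP 6.3 conflicts with protocol Table 1, with SAP Appendix 1 and with SAP 3.2.5. The consequence is conditional. If the Part A tables and shifts are programmed from the listed visits without the period cut-off, every scheduled Day 183 lipid value in the Placebo column would come from a subject already on PTC857, for about 14 days if open-label dosing starts at Day 169. Those subjects' last or worst on-treatment lipid grade could then also be an open-label value. If section 3.2.5 is applied, none of this happens and the listed Day 183 visit is simply void. At Day 197 the expected result under the note is empty cells.

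The number affected cannot be computed; about 113 is a ceiling. The tables are descriptive, with no between-group tests, and neither the primary nor any other efficacy analysis is touched. Severity is minor.

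**What to change.** In section 6.3 of the Part A SAP:

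1. Delete Day 183 from the lipid row.
2. Delete Day 197 from the hematology, chemistry, lipid and coagulation rows. Keep it in the pregnancy-test row.
3. State that Part A laboratory summaries, and the shifts to last and worst on-treatment grade, exclude any value on or after the first open-label dose, except pre-dose values at the Day 169 visit.

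The exception in item 3 is needed because section 3.2.5, read literally, ends the period the day before the first open-label dose. A subject whose first open-label dose falls on Day 169 would otherwise lose a valid end-of-treatment sample taken that morning.

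The Day 183 and Day 197 values stay in the Parts B/C SAP. The cost is a few words in the SAP and one date filter in the laboratory programs. No new data are needed, and the times at which blood is drawn do not change.
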